3.3. Blinding

Site staff and blinded sponsor team members will be blinded to treatment allocation (BGB-290 or placebo).

Unblinding of a patient's treatment assignment may be performed at any time and without restrictions based on the investigator's (or other non-study treating physician's) clinical judgement if the knowledge of the treatment arm is essential for the further management of the patient.

The investigator can access the IRT system using assigned credentials to immediately perform unblinding. Following unblinding, the system will notify the sponsor of unblinding of the patient without revealing the patient's treatment assignment. In the event that the investigator is not available to perform unblinding, each randomized patient is provided with a patient information card that includes a global phone number linked to an after-hours physician-staffed emergency medical service. Additionally, the card provides a unique, blinded number that links to the subject's treatment arm.

Any physician treating a patient that is participating in the study (eg, emergency room physician or other health care provider [HCP] unaffiliated with the study) can contact the emergency medical service to unblind the patient using the information located on the patient information card. The emergency service will perform this unblinding and inform the treating physician/HCP of the patient's treatment assignment. If unblinding occurs, the service will provide notification to the sponsor of the patient-specific unblinding without revealing the patient's treatment assignment.

3.4. Duration of the Study

The duration of the study from first enrolled patient until final analysis is estimated to be 2.5 years.

4. STUDY POPULATION

4.1. Inclusion Criteria

Patients must meet all of the following criteria to be eligible for the study:

1. Signed informed consent form (ICF)
2. Age \geq 18 year
3. Histologically proven adenocarcinoma of the stomach or gastroesophageal junction, inoperable locally advanced or with metastatic disease
 - a. Patients with gastric cancer overexpressing HER2 are not allowed.

- Negative result for HER2, as determined by local assessment, must be documented in order for a patient to be eligible.
 - b. Irradiation as part of prior first-line treatment is not allowed.
4. Availability of archival tumor tissue for central laboratory determination of HRD status for randomization and exploratory biomarker analyses
 - Tumor tissue needs to originate from core or punch biopsy.
 - Tumor tissue from fine-needle aspiration is not acceptable.
 5. Received platinum-based first-line chemotherapy with a total of ≥ 8 platinum-containing 14-day cycles, ≥ 5 platinum-containing 21-day cycles, or ≥ 4 platinum-containing 28-day cycles for ≤ 28 weeks
 6. Confirmed PR that is maintained for ≥ 4 weeks or CR as determined by the investigator per RECIST Version 1.1 ([Appendix 2](#))
 7. Ability to be randomized ≤ 8 weeks after last dose of platinum
 8. ECOG performance status ≤ 1 ([Appendix 3](#))
 9. Ability to swallow whole capsules
 10. Ability to comply with study requirements and complete study questionnaires independently
 11. Adequate hematologic and end-organ function, as defined by the following laboratory results (obtained ≤ 14 days before randomization):
 - a. Absolute neutrophil count (ANC) $\geq 1.5 \times 10^9/L$
 - b. Platelet count $\geq 100 \times 10^9/L$
 - c. Hemoglobin ≥ 9 g/dL (≥ 14 days after growth factor support or transfusion)
 - d. Estimated glomerular filtration rate ≥ 30 mL/min/1.73 m² by the Modification of Diet in Renal Disease study equation (MDRD STUDY EQ; www.mdrd.com or [Appendix 11](#))
 - e. Total serum bilirubin $\leq 1.5 \times$ upper limit of normal (ULN)
 - $\leq 4 \times$ ULN, if Gilbert's syndrome or if indirect bilirubin concentrations suggestive of extrahepatic source of elevation
 - f. Aspartate and alanine aminotransferase (AST and ALT) $\leq 3 \times$ ULN
 12. Females of childbearing potential, nonsterile males, and female partners of nonsterile male study patients must agree to practice highly effective methods of birth control ([Appendix 4](#)) for the duration of the study and for at least 6 months after last study drug. Nonsterile males must avoid sperm donation for the duration of the study and for at least 6 months after last study drug.

4.2. Exclusion Criteria

Patients will be excluded from the study for any of the following reasons:

1. Unresolved acute effects of prior therapy of \geq Grade 2
 - Except for AEs not considered a likely safety risk (eg, alopecia, neuropathy and specific laboratory abnormalities)
2. Prior treatment with a PARP inhibitor
 - Subtherapeutic exposure to a PARP inhibitor for \leq 28 days is permissible provided it was not the most recent prior therapy.
3. Chemotherapy, biologic therapy, immunotherapy, investigational agent, anticancer Chinese medicine, or herbal remedies \leq 14 days (or \leq 5 half-lives, whichever is shorter) before randomization
 - Bisphosphonate and denosumab use is allowed on study, if administered at a stable dose $>$ 28 days before randomization.
4. Major surgical procedure, open biopsy, or significant traumatic injury \leq 14 days before randomization, or anticipation of need for major surgical procedure during the course of the study
 - Placement of vascular access device is not considered major surgery.
5. Diagnosis of MDS
6. Other diagnosis of malignancy
 - Except for surgically excised nonmelanoma skin cancer, adequately treated carcinoma in situ of the cervix, localized prostate cancer treated with curative intent, adequately treated low-stage bladder cancer, ductal carcinoma in situ treated surgically with curative intent, or a malignancy diagnosed $>$ 2 years ago with no current evidence of disease and no therapy \leq 2 years before randomization
7. Leptomeningeal disease or brain metastasis
8. Active infection requiring systemic treatment, active viral hepatitis, or active tuberculosis
9. Any of the following cardiovascular criteria:
 - a. Cardiac chest pain, defined as moderate pain that limits instrumental activities of daily living, \leq 28 days before randomization
 - b. Symptomatic pulmonary embolism \leq 28 days before randomization
 - c. Any history of acute myocardial infarction \leq 6 months before randomization
 - d. Any history of heart failure meeting New York Heart Association Classification III or IV ([Appendix 5](#)) \leq 6 months before randomization

- e. Any event of ventricular arrhythmia \geq Grade 2 in severity \leq 6 months before randomization
 - f. Any history of cerebral vascular accident \leq 6 months before randomization
10. Previous complete gastric resection, chronic diarrhea, active inflammatory gastrointestinal disease, or any other disease causing malabsorption syndrome
- Gastroesophageal reflux disease under treatment with proton pump inhibitors is allowed.
11. Active bleeding disorder, including gastrointestinal bleeding, as evidenced by hematemesis, significant hemoptysis, or melena \leq 6 months before randomization
12. Use \leq 10 days (or \leq 5 half-lives, whichever is shorter) before randomization or anticipated need for food or drugs known to be strong or moderate cytochrome P450 (CYP) 3A inhibitors or strong CYP3A inducers ([Appendix 6](#))
13. Pregnancy or nursing
- a. Females of childbearing potential require a negative serum pregnancy test \leq 7 days before randomization.
14. Significant intercurrent illness that may result in the patient's death before death from gastric cancer
15. Known history of intolerance to the excipients of the BGB-290 capsule

5. STUDY PHASES FROM SCREENING TO END OF STUDY

5.1. Screening

As part of the screening visit, study center personnel will explain to the potential patient all aspects of the study, obtain signed informed consent, and document the informed consent process in the patient's source documents before any study-specific procedures are conducted.

The signed ICF initiates screening that must occur within 28 days of randomization (Day -28 to Day -1). Study center personnel will access the Interactive Response Technology (IRT) system to obtain a screening identification number for the potential patient.

Required screening assessments, some with shorter screening windows, are listed in [Appendix 1](#). Assessments obtained within 7 days of Day 1 do not have to be repeated on Day 1. Patient registration and randomization may occur as late as Day 1 before any study treatment. Results of standard of-care tests or examinations performed before obtaining informed consent and within the screening windows may be used and do not have to be repeated as long as they meet protocol specifications.

The investigator and site radiologist will assess the potential patient for eligibility. Repeating screening assessments within the original screening window is allowed if the patient did not

previously meet certain eligibility criteria. Screen failures and consent withdrawals will be documented in the patients' source documents.

5.2. Enrollment

After consent has been obtained, each patient will be assigned a unique patient number by the IRT system that cannot be reassigned to any other patient. After determination of eligibility, the investigator will complete the randomization request form and supporting documentation and provide them to the sponsor and/or designee for review and subsequent approval in the IRT system. No eligibility waivers will be granted.

After medical monitor approval, the investigator or delegate will access the IRT system for randomization of the patient based on the protocol-specified stratification factors. The randomization list will be kept by the IRT vendor in their secure system and will not be accessible to the study center, responsible (or designee) monitors, project statisticians, or to the blinded project team at BeiGene, Ltd. (hereafter referred to as BeiGene). Blinded team members will not have access to unblinded information in IRT; this will be managed by clearly defined roles and permissions within the IRT system.

5.3. Treatment

Day 1 of Cycle 1 is the first day of study drug administration (there is no Day 0 in this protocol). Patients must initiate study treatment within 4 days after randomization.

Study procedures of each clinic visit are outlined in [Appendix 1](#).

On days with PK assessments, study drug should be administered in the clinic in accordance with the schedule for the PK samples. Assessments should be obtained before study drug administration unless stated otherwise in [Appendix 1](#) and should be performed in order of least invasive to most invasive assessment. All safety-related assessments must be reviewed and dose modifications, if necessary, be made by the investigator or subinvestigator before study drug administration.

Patient-reported outcome questionnaires should be completed before any other study activities occur.

5.4. Unscheduled Visit

Unscheduled visits may occur any time as necessary as per investigator decision or patient's request for reasons such as assessment or follow-up of AEs. Study activities of an unscheduled visit should be performed based on the reason for the unscheduled visit and are outlined in [Appendix 1](#). If PD is suspected, imaging studies should be performed and blood for biomarkers should be obtained as appropriate.

5.5. Permanent Discontinuation of Study Drug

5.5.1. Reasons for Permanent Discontinuation of BGB-290 or Placebo

Patients may permanently discontinue BGB-290 or placebo for any of the following reasons:

- PD
- AEs
- Pregnancy
- Major protocol deviation
- Patient withdrew consent for study treatment
 - Patients may voluntarily withdraw consent from study treatment at any time
 - Patients should be requested to participate in the follow-up phase, if patient withdraws consent from the treatment phase only
- Investigator's discretion
- Start of new anticancer therapy

The reason for permanent discontinuation of BGB-290 or placebo will be recorded on the electronic case report form (eCRF). Patients may discontinue study drug for other reasons but these will result in premature discontinuation from study (Section 5.7) and, consequently, result in lack of an EOT visit.

5.5.2. End of Treatment Visit

The EOT visit should occur within 7 days after BGB-290 or placebo has been permanently discontinued. Required assessments are listed in [Appendix 1](#). A visit should be scheduled as soon as possible, but the EOT visit may occur later after discussion with the medical monitor for specific circumstances, such as prolonged hospitalization. The visit at which tumor assessments showed PD may be used as the EOT visit providing all required assessments were performed. Tumor assessments do not have to be repeated if they were performed within 14 days of the EOT visit or at a prior response evaluation that documented PD. An ECG does not have to be repeated if it was performed within 14 days of the EOT visit.

5.6. Follow-Up Phase

5.6.1. Safety Follow-up

All patients who permanently discontinue study drug and have not initiated new anticancer therapy will be followed for AEs and serious AEs (SAEs) as outlined in Section 9.3.1. Approximately 30 days after the last day of study drug or before initiation of new anticancer therapy, whichever occurs first, a safety follow-up will occur with the safety assessments outlined in [Appendix 1](#). If new anticancer therapy is inadvertently initiated before this safety follow-up (eg, without the knowledge of the study center team), a safety follow-up should be scheduled as soon as possible.

For patients who do not want to or cannot return to the clinic for the safety follow-up, the patient should be contacted by telephone for a review of AEs. If these attempts of contact are unsuccessful, the additional attempts detailed in Section 5.6.3 should be made.

5.6.2. Long-term Follow-up

Patients will be followed for survival, further anticancer therapy, and diagnosis of MDS or AML via telephone contact or other means (eg, clinic visit) approximately every 12 weeks until death, withdrawal of consent, or the end of study, whichever occurs first ([Appendix 1](#)).

Patients who were permanently discontinued from study drug for reasons other than PD and meet criteria otherwise (eg, discontinued for AE and no new anticancer therapy) will be followed with tumor assessments every 8 weeks (± 7 days) until PD or any other reason listed in [Section 5.7](#), whichever occurs first. For efficacy assessments as per protocol, refer to [Section 7.3.2](#) and [Appendix 1](#). If the patient refuses to return for these tumor assessments or is unable to do so, every effort should be made to contact the patient by telephone to determine the patient's disease status and survival.

5.6.3. Lost to Follow-up

If attempts to contact the patient by telephone are unsuccessful, the following additional attempts should be made to obtain protocol-required follow-up information. The patient should be contacted by mail in a manner that provides proof of receipt by the patient. If unsuccessful, other contacts should be explored, such as referring physicians or relatives. Attempts of contact should be documented in the patient's source documents. If a patient cannot be contacted despite all attempts, the patient will be considered lost to follow-up, and death information should be obtained through a public record search if local agencies permit.

5.7. End of Study

Premature discontinuation from the study (without EOT and any follow-up visits) will occur under the following circumstances:

- Patient withdrew consent for study participation
 - Patients may voluntarily withdraw consent from the study at any time
- Investigator's discretion
- Lost to follow-up
 - Lost to follow-up should be recorded as such in the eCRF
 - The investigator should show due diligence by documenting in the source documents steps taken to contact the patient ([Section 5.6.3](#))
- Death
- Study termination by sponsor
- Other, as per the discretion of the sponsor or health authority

6. STUDY TREATMENT

6.1. Study Drug

6.1.1. Packaging and Labeling

BGB-290 is provided in 20-mg capsules or matching placebo. BGB-290 and placebo capsules will be provided in 30-count child-resistant high-density polyethylene bottles with an induction seal and bottle label. The contents of the label will be in accordance with all applicable local regulatory requirements. The label will include at a minimum: drug name, dose strength, contents, sponsor, protocol number, bottle number, directions for use, storage conditions, caution statements, retest or expiration date, and space to enter the patient number and name of investigator.

6.1.2. Handling and Storage

The instructions for drug ordering are in the pharmacy binder. The IRT system will also be used for drug supply management. The study drug will be dispatched to a study center only after receipt of the required documents in accordance with applicable regulatory requirements and the sponsor's procedures. The investigator or pharmacist/designated personnel is responsible for maintaining the drug supply inventory and acknowledging receipt of all study drug shipments. All study drugs must be stored in a secure area with access limited to the investigator and authorized study center personnel and under physical conditions that are consistent with study drug specific requirements.

The study drugs must be kept at the condition as specified on the labels. BGB-290 and placebo bottles must be stored at 15°C to 30°C (59°F to 86°F) and protected from light.

6.1.3. Dosage and Administration

Both BGB-290 and placebo capsules will be administered PO BID, once in the morning and once in the evening. The time difference between 2 consecutive doses should be approximately 8 to 12 hours.

Patients will be instructed to swallow the capsules whole, in rapid succession, with water. BGB-290 can be administered with or without food.

A dose of BGB-290 or placebo should be skipped if it is not taken within 2 hours of the scheduled time. An extra dose of BGB-290 or placebo should not be taken to make up for a missed dose. If vomiting occurs during the course of treatment, no re-dosing of the patient is allowed before the next scheduled dose.

On days with PK assessments, BGB-290 or placebo should be administered in the clinic in accordance with the schedule for the PK samples ([Appendix 1](#)).

6.1.4. Dose Hold and Modification

AEs should be assessed as best as possible regarding their relatedness to BGB-290 or placebo. Investigators should assess all patients as if they were receiving BGB-290. Regardless of

discontinuation of BGB-290 or placebo, patients should continue on study with follow-up as outlined in Sections 5.5 and 5.6.

Investigators should make every effort to maintain dose intensity in patients. Dosing of BGB-290 or placebo can be withheld for up to 28 days consecutively. If drug is planned to be held > 28 days, the medical monitor should be contacted before permanent patient discontinuation from the study drug.

Criteria for treatment modifications and suggested guidelines for the management of some toxicities related to BGB-290 or placebo are summarized below. These general guidelines may be modified at the discretion of the investigator based on discussions with the medical monitor and the best clinical judgment at that time; any decisions should be documented. Any toxicities related to BGB-290 or placebo should be managed according to standard medical practice.

A maximum of 2 dose reductions is allowed before the patient must be permanently withdrawn from study drug. Dose levels for BGB-290 or placebo are summarized in Table 2. BGB-290 or placebo will be dose modified as outlined in Table 3.

Table 2: Dose Levels for BGB-290 and Placebo

Dose Level	BGB-290	Placebo
1	60 mg PO BID	60 mg PO BID
-1	40 mg PO BID	40 mg PO BID
-2	20 mg PO BID	20 mg PO BID

Abbreviations: PO, oral; BID, twice daily.

BGB-290 may be dose-reduced for a maximum of 2 dose reductions.

Table 3: Criteria for Modification of BGB-290 or Placebo Dosing for Related Adverse Events

Toxicity	Recommended Dose Modification ^a
Hematologic	
Anemia (hemoglobin, Hgb)	
Grade 2 (Hgb < 10 - 8 g/dL) Only applies to patients with normal Hgb at baseline	First occurrence: continue dosing at current dose level Second and subsequent occurrences: hold BGB-290 or placebo until resolved to ≤ Grade 1 or baseline 
 • If resolved ≤ 14 days, then maintain dose levels • If resolved > 14 days, then ↓ BGB-290 or placebo by 1 dose level
Grade 3 (Hgb < 8 g/dL)	Hold BGB-290 or placebo until resolved to ≤ Grade 1 or baseline 
 • If resolved ≤ 14 days, then maintain dose levels • If resolved > 14 days, then ↓ BGB-290 or placebo by 1 dose level
Grade 4 (life-threatening consequences; urgent intervention indicated)	Hold BGB-290 or placebo until resolved to ≤ Grade 1 or baseline and ↓ BGB-290 or placebo by 1 dose level
Neutropenia (absolute neutrophil count, ANC)	
Grade 3 (ANC < 1.0 - 0.5 × 10 ⁹ /L)	Hold BGB-290 or placebo until resolved to ≤ Grade 2 or baseline 
 • If resolved ≤ 7 days, then maintain dose levels • If resolved > 7 days, then ↓ BGB-290 or placebo by 1 dose level
Grade 4 (ANC < 0.5 × 10 ⁹ /L)	Hold BGB-290 or placebo until resolved to ≤ Grade 1 or baseline and ↓ BGB-290 or placebo by 1 dose level
Febrile neutropenia (ANC < 1.0 × 10 ⁹ /L with single temperature of > 38.3°C or sustained temperature of ≥ 38°C for > 1 hour)	Hold BGB-290 or placebo until resolved and ↓ BGB-290 or placebo by 1 dose level
Thrombocytopenia (platelet count, PLT)	
Grade 3 (PLT < 50 - 25 × 10 ⁹ /L)	Hold BGB-290 or placebo until resolved to ≤ Grade 1 or baseline 
 • If resolved ≤ 7 days, then maintain dose levels • If resolved > 7 days, then ↓ BGB-290 or placebo by 1 dose level
Grade 4 (PLT < 25 × 10 ⁹ /L)	Hold BGB-290 or placebo until resolved to ≤ Grade 1 or baseline and ↓ BGB-290 or placebo by 1 dose level
Renal	
Estimated glomerular filtration rate (MDRD STUDY EQ; www.mdrd.com or Appendix 11)	
If ≥ 60 mL/min/1.73 m ² at baseline: < 30 to 15 mL/min/1.73 m ² or If < 60 mL/min/1.73 m ² at baseline: ≥ 50% reduction from baseline	Hold BGB-290 or placebo until resolved to ≥ 60 mL/min/1.73 m ² 
 • If resolved ≤ 7 days, then maintain dose levels • If resolved > 7 days, then ↓ BGB-290 or placebo by 1 dose level
Regardless of baseline: < 15 mL/min/1.73 m ²	Permanently discontinue BGB-290 or placebo

Table 3: Criteria for Modification of BGB-290 or Placebo Dosing for Related Adverse Events

Toxicity	Recommended Dose Modification^a
Hepatic	
Bilirubin	
Grade 2 (> 1.5 - 3.0 × ULN) Only applies to patients with normal bilirubin at baseline	Hold BGB-290 or placebo until resolved to ≤ Grade 1 or baseline 
 • If resolved ≤ 7 days, then maintain dose levels • If resolved > 7 days, then ↓ BGB-290 or placebo by 1 dose level
Grade 3 (> 3.0 - 10.0 × ULN)	Hold BGB-290 or placebo until resolved to ≤ Grade 1 or baseline 
 • If resolved ≤ 7 days, then maintain dose levels • If resolved > 7 days, then ↓ BGB-290 or placebo by 1 dose level
Grade 4 (> 10.0 × ULN)	Permanently discontinue BGB-290 or placebo Note: If Grade 3 or 4 hyperbilirubinemia is due to the indirect (unconjugated) component only, and hemolysis as the etiology has been ruled out as per institutional guidelines (eg, review of peripheral blood smear and haptoglobin determination), then ↓ BGB-290 or placebo by 1 dose level and continue treatment at the discretion of the investigator in discussion with the medical monitor
Aspartate aminotransferase (AST) and/or alanine aminotransferase (ALT)	
Grade 3 (> 5 and ≤ 20 × ULN)	Hold BGB-290 or placebo until AST and/or ALT resolved to ≤ 5 × ULN or baseline 
 • If ≤ 5 × ULN within 14 days, then ↓ BGB-290 or placebo by 1 dose level • If second episode, permanently discontinue BGB-290 or placebo • If persistent for >14 days, permanently discontinue BGB-290 or placebo
Grade 4 (> 20 × ULN)	Permanently discontinue BGB-290 or placebo
Pancreatic	
Pancreatitis	
Grade 3 or 4	Permanently discontinue BGB-290 or placebo
Cardiac	
Cardiac - Prolonged QTc interval	
QTcF > 500 msec	
 • Obtain triplicate ECGs (2 to 3 minutes apart) ~1 hour after initial ECG • If mean QTcF > 500 ms, hold BGB-290 or placebo until evaluation of ECGs by cardiologist 
 ○ Cardiology evaluation as soon as practical but within 7 days of initial abnormal ECG • If mean QTcF > 500 ms confirmed by cardiologist, permanently discontinue BGB-290 or placebo
Cardiac - General	
Grade 3	Hold BGB-290 or placebo until resolved to ≤ Grade 1 or baseline and ↓ BGB-290 or placebo by 1 dose level
Grade 4	Permanently discontinue BGB-290 or placebo

Table 3: Criteria for Modification of BGB-290 or Placebo Dosing for Related Adverse Events

Toxicity	Recommended Dose Modification ^a
Other adverse events	
Grade 3	Hold BGB-290 or placebo until resolved to ≤ Grade 1 or baseline and ↓ BGB-290 or placebo by 1 dose level No dose reduction required for asymptomatic laboratory abnormalities
Grade 4	Permanently discontinue BGB-290 or placebo

Abbreviations: ECG, electrocardiogram; MDRD, Modification of Diet in Renal Disease; QTcF, QT interval corrected for heart rate using Fridericia’s formula; ULN, upper limit of normal.

a. Dosing of BGB-290 or placebo can be withheld for up to 28 days consecutively.

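### Protocol Table 3 (Renal): a patient entering with eGFR 30-59 who recovers fully from a renal hold still does not meet the written rule for resuming drug

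*Protocol*

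**What the plan says.** Inclusion criterion 11d (Protocol 4.1) sets the entry floor for eGFR at 30 mL/min/1.73 m², so patients with baseline 30-59 are eligible.

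Table 3 in Protocol 6.1.4 is titled "Criteria for Modification of BGB-290 or Placebo Dosing for Related Adverse Events", so it covers related events only. Its renal row has two hold triggers. With baseline 60 or more, the trigger is a fall to below 30, down to 15. With baseline below 60, the trigger is worded "at baseline: ≥ 50% reduction from baseline". Both triggers lead to one action: hold "until resolved to ≥ 60 mL/min/1.73" m². Two bullets follow. The first reads "If resolved ≤ 7 days, then maintain dose levels"; the second reduces the dose by one level if resolution takes more than 7 days. A further row, "Regardless of baseline: < 15 mL/min/1.73" m², requires permanent discontinuation.

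The text of 6.1.4 limits the hold: "Dosing of BGB-290 or placebo can be withheld for up to 28 days consecutively". If a longer hold is planned, "the medical monitor should be contacted before permanent patient discontinuation from the study drug". It also allows departures from the table: "These general guidelines may be modified at the discretion of the investigator based on discussions with the medical monitor", with the decision documented.

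**The concern.** The table recognises that some patients start below 60 and gives them a trigger relative to their own baseline. It then asks them to reach a level they did not have when they started treatment. Read literally, a patient who regains all lost renal function stays on hold toward the 28-day limit. Neither 7-day bullet can be used, because both presuppose resolution. At stake is avoidable loss of dosing in recovered patients, and reliance on case-by-case discussion where the table was meant to give the answer.

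A second, smaller inconsistency is in the same place. Inclusion 11d and the renal header of Table 3 both name the MDRD equation and cite Appendix 11, but that appendix is titled and written for CKD-EPI and prints only that formula.

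**Working it through.** The plan states no statistical figure on this point, so there is none to reproduce. The check is of thresholds.

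**Inputs** (eGFR in mL/min/1.73 m²; B is the patient's baseline)
- Entry floor 30: Protocol 4.1, inclusion 11d.
- Hold trigger for B below 60, a fall of at least 50%: Table 3, Renal.
- Resume level 60 for both branches: Table 3, Renal.
- Permanent discontinuation below 15: Table 3, Renal.

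**Formulas for B below 60**
- Hold window: from 15 to 0.5 × B, with width 0.5 × B − 15.
- Resume level as a share of baseline: 60 / B.
- Share of lost function to regain, from the top of the window: (60 − 0.5B) / (0.5B).
- The same share from the bottom of the window: (60 − 15) / (B − 15).

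| B | Hold window | Width | 60 / B | Share to regain, from top | Share to regain, from 15 |
|---|---|---|---|---|---|
| 30 | 15 only | 0 | 200% | 300% | 300% |
| 40 | 15-20 | 5 | 150% | 200% | 180% |
| 45 | 15-22.5 | 7.5 | 133% | 167% | 150% |
| 50 | 15-25 | 10 | 120% | 140% | 129% |
| 59 | 15-29.5 | 14.5 | 102% | 103% | 102% |

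For example, at B = 40 the patient must reach 60/40 = 150% of baseline. From 20, that is (60 − 20)/20 = 200% of the function lost. Full recovery is 100% in the last two columns, and every entry exceeds it. The test that B is at least 60 fails throughout this branch.

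**The other branch.** For B = 60, 75, 90 and 120, the resume level is 100%, 80%, 67% and 50% of baseline. It never asks for more than the patient's own baseline, so the rule works there.

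**Comparison within Table 3.** Twelve hold rules accept return to baseline as an alternative: anemia Grades 2, 3 and 4; neutropenia Grades 3 and 4; thrombocytopenia Grades 3 and 4; bilirubin Grades 2 and 3; AST/ALT Grade 3; general cardiac Grade 3; other events Grade 3. The three holds without it are febrile neutropenia (resolution only), QTc (cardiologist evaluation) and renal. Renal is the only one of these three with a numeric laboratory threshold.

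The anemia Grade 3 row shows why the alternative is needed. Inclusion 11c admits hemoglobin of 9 g/dL or more, and Grade 2 begins below 10. A patient entering at 9.0-9.9 therefore starts below the Grade 1 resume level and can resume only because return to baseline also counts. A patient entering at eGFR 30-59 is in the same position without that option.

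**The case against.** The strongest reply is that the protocol already provides a way out. The table column is headed as a recommendation, and 6.1.4 calls the material general guidelines that may be changed after documented discussion with the medical monitor. Section 6.1.4 also asks investigators to make every effort to keep up dose intensity, which favours resuming. This stands as a limit on harm: the patient can resume within the protocol. It does not repair the rule. The same section says dosing will be modified as Table 3 sets out, and here the default fails for a whole branch that the table created on purpose.

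The reach is small. A case needs a baseline of 30-59, a fall of at least half, an eGFR still at 15 or above, and an event judged related. Where the resume gap is largest, the window is almost closed (B = 30); where the window is widest, the gap is about 1 unit (B = 59). The Phase 1 summary in Protocol 1.4.2.3 lists no renal event among the common related events or the related Grade 3 events. All of this stands.

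The level of 60 could also be deliberate caution after a large renal loss. The documents give no such reason. They allow full-dose treatment to start at 30-59, state permanent discontinuation where it is wanted, and attach 7-day rules that assume dosing will restart. Still, the correction has a consequence. A patient with baseline 35 who falls to 17 and returns to 35 within 7 days would restart at the same dose without discussion. Whether that is acceptable is a clinical judgment, although the same bullet already applies to patients with baseline 60 or more. Near-complete recovery, such as 49 from a baseline of 50, would still need discussion.

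The equation reference is a separate matter and adds no weight to the dosing point.

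**Conclusion.** The concern holds. For every baseline from 30 up to but not including 60, full return to baseline fails the only written resume criterion, and neither 7-day instruction can be applied. The level demanded runs from 200% of baseline at 30 (where the hold window is the single value 15) to 102% at 59.

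This rests on a literal reading of Table 3 and needs no outside figure. The number of patients affected cannot be estimated, because the documents do not give the share entering at 30-59. The consequence is confined to dosing after related renal events. The rule is the same in both blinded arms, and no endpoint, alpha or power changes. It should be corrected, but it does not threaten the trial's conclusions.

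The MDRD/CKD-EPI mismatch is a genuine reference error. The size of its effect cannot be computed from the documents.

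**What to change.** In the renal cell of Table 3, let return to baseline count as resolved: 60 mL/min/1.73 m² or more, *or baseline*. Nothing changes for patients with baseline 60 or more, because their baseline already meets the threshold. If the sponsor's clinical team wants a dose reduction or a mandatory discussion after recovery in the below-60 branch, the table should say so.

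Separately, name one equation consistently in inclusion 11d, Table 3 and Appendix 11. Which one is for the clinical team to decide.

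The cost is two words in one table cell and one corrected reference, with no change to assessments, endpoints or analysis. Protocol 11.3.1 requires modifications to go to regulatory authorities and the IRB/IEC, and there are approximately 110 centers, so this belongs in the next amendment rather than one of its own. SAP section 8 describes enrolment in the past tense, so the eligibility part of the equation correction may have little remaining use. The dosing cell matters as long as patients stay on drug, which may include those kept on BGB-290 within this study after unblinding (Protocol 3.1).
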